## 13.0 CRITERIA FOR REMOVAL FROM STUDY

- 13.1 Development of clear-cut evidence of recurrent colorectal cancer in the liver compared to the baseline postoperative CT scan, via clinical exam or imaging studies. These patients will still be followed for recurrence and survival.

- 13.2 Development of clear-cut evidence of extrahepatic recurrence via clinical exam or imaging studies. These patients will still be followed for recurrence and survival.
- 13.3 Patient is unable to resume hepatic arterial FUDR due to hepatic toxicity. These patients will still be followed for recurrence and survival.
- 13.4 Unacceptable toxicity that does not respond to the dosage modification. Even if patients cannot tolerate treatment they will be continued to be followed for survival and recurrence.
- 13.5 Patient elects to discontinue treatment.
- 13.6 Changes in a patient's condition which render the patient unacceptable for further treatment in the judgment of the investigator. These patients will still be followed for recurrence and survival.

#### **14.0 BIOSTATISTICS**

This study will 1:1 randomize 78 patients to two treatment arms: HAI FUDR and dexamethasone with systemic chemotherapy, +/- systemic Panitumumab. Randomization procedures will be discussed in section 15.2.

The primary endpoint is 15 month recurrence free survival (RFS). Based on an exact binomial single stage design, with 39 patients in each arm we are able to differentiate between unacceptable 15 month RFS of 50% and acceptable 15 month RFS of 70% with type I error (falsely accepting a non-promising therapy) and II error (falsely rejecting a promising therapy) rates of 10 % each. For a particular arm, if 24 or more patients are alive and disease free at 15 months the regimen in that arm will be considered worthy of further investigation. We will use the —pick the winner— format based on the randomized phase II clinical trials approach proposed by Simon et al. (1985) to differentiate between 15 month RFS of 50% and 70%. The pick the winner role only occurs if both regimens are efficacious. If the number of patients who are disease free and alive at 15 months in one arm is at least 24 and it exceeds by at least 3 patients the number of alive and disease free patients at 15 months in the other arm, then the arm with the higher 15 months RFS would be declared the winner. If neither arm had at least 24 patients alive and disease free at 15 months, the regimens in both arms would be considered unworthy of further evaluation. The probability of selecting the better regimen is 85%; the probability that no regimen is selected is approximately 9%, while the probability of a tie is 6 % (Simon R, Wittes RE, Ellenberg SS. (1985). Randomized phase II clinical trials. *Cancer Treat Rep* 69, 1375-1381.)

RFS will also be estimated using the Kaplan Meier method. As secondary endpoint, overall survival will be estimated by the Kaplan Meier method. Associations between biomarkers and RFS and overall survival will be assessed using the log-rank test. In each arm, safety and tolerability will be summarized using descriptive statistics.

The prevalence of RAS mutations is about 40%; therefore we would have to approach about 120 patients in order to accrue 78 patients. On average, we see about 40 eligible patients per year; therefore we would need three years to reach 120.

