## 1.0 PROTOCOL SUMMARY AND/OR SCHEMA

### Study Objective

- The primary objective of the study is to determine if panitumumab with hepatic arterial infusion (HAI) in combination with systemic chemotherapy can increase the recurrence free survival (RFS) for colorectal cancer patients with resected liver metastases.

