### Therapeutic Intervention

- All patients receive HAI FUDR (0.12 mg/kg/day X kg X pump volume) / pump flow rate and Dexamethasone flat dose of 25 mg on days 1.
- All patients receive CPT-11 (150 mg/m^2 IV over 30 min to an hour), Leucovorin (400 mg/m^2 IV over 30 min to an hour) and 5FU (1000 mg/m^2/day continuous infusion over two days) on days 15 and 29
- Randomization to panitumumab 6 mg/kg day 15 and 29 (or no panitumumab)
- Each cycle repeats every 36 days for a total of 6 cycles.

This phase II study aims to assess the efficacy of panitumumab with HAI in combination with systemic chemotherapy in patients with completely resected hepatic metastases from colorectal cancer. The protocol includes biological correlative studies. The primary objective of this study is to determine if the RFS increases with the addition of concurrent intravenous Panitumumab to HAI plus systemic chemotherapy after hepatic resection. This study will 1:1 randomize 78 patients who are all-RAS wild type after liver resection to HAI FUDR and dexamethasone with systemic chemotherapy, +/- systemic Panitumumab. The primary endpoint is 15 month RFS.

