## 2.0 OBJECTIVES AND SCIENTIFIC AIMS

- The primary objective of the study is to determine if panitumumab with HAI in combination with systemic chemotherapy can increase the 15 month RFS for colorectal cancer patients with resected liver metastases.
- The secondary objectives are (1) to assess toxicity, (2) to determine survival, (3) to analyze tumor tissue for predictive biomarkers (such as NRAS, BRAF, PIK3CA, AKT1 and MEK1), and correlate with patient progression and survival following therapy. Most patients will have had RAS testing performed prior to protocol treatment; RAS will be analyzed at surgery if not performed previously. Frozen and paraffin-fixed tissue from the liver metastases will be available at surgery to measure these values.

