Modern chemotherapy such as irinotecan in combination with HAI FUDR/ Dexamethasone (Dex) in a phase I/II trial after resection of liver metastases yielded a 5 year survival of 59%. In a phase I trial with oxaliplatin + FU/LV added to HAI FUDR/Dex after liver resection, the 4 year overall survival was 88%. Alberts and colleagues reported results from the NSABP study of systemic capecitabine and oxaliplatin alternating with HAI FUDR after resection of liver metastases. The 2 year survival rate was 88% (95% CI 82-98%) with a median follow-up of 4.8 years. The 2 year overall recurrence was 59.7 %.

In a retrospective review, House et al evaluated patients who underwent liver resection between 2001-2005 and compared 125 patients who were treated with HAI plus modern systemic chemotherapy with those who received modern chemotherapy alone. They reported a 5 year survival of 72% and 52% (p=0.004) for the 2 groups, respectively. In a larger retrospective review at MSKCC of over 1,000 patients who underwent liver resection, a multivariate analysis demonstrated that one of the most significant factors leading to improved survival was postoperative HAI therapy. Those who received HAI therapy after hepatic resection had a median survival of 68 months versus 50 months for those who did not (p<0.001).

In our last four adjuvant studies, the patient population has been changing. Our surgeons are resecting patients with more disease. As we accrue patients with worse prognostic factors, the recurrence-free survival is decreasing. The table below reflects these characteristics.

Variables		HAI + 5FU/LV (n = 74) %	HAI + CPT-11 (n = 96) %	HAI + FOLFOX (n = 37) %	HAI + FOLFOX or FOLFIRI, +/- BEV (n = 73) %
# lesions (Pathology)	1	36	40	32	23
	2-4	45	47	57	43
	>4	19	13	11	33
Lesion Size	≥ 5cm	30	25	22	18
DFI	< 12 mos	77	74	62	79
Margins	≤ 1 mm	23	11	11	16

+ Margins	0 mm	15	4	5	10
Post-op CEA	> 5 ng/ml	26	33	16	21

Because of the increase in poor patient characteristics, the recurrence-free survival in our most recent study with HAI depicted above by the red line appeared to be inferior to previous adjuvant studies conducted at MSKCC with HAI (RFS was 59 % at 15 months). This is compared with a RFS of approximately 40 % at 15 months from recent studies evaluating systemic therapy (as reflected in the chart in section 2.1.1).

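### The objective asks whether panitumumab increases RFS, but section 14 compares the arms only by a selection rule, plans no between-arm estimate, and contains one sentence that contradicts that rule

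*Combined protocol and SAP*

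**What the plan says.** Section 1.0 (Therapeutic Intervention) gives the primary objective as to "determine if the RFS increases with the addition of concurrent intravenous Panitumumab to HAI plus systemic chemotherapy". Section 2.0 words it as to "determine if panitumumab with HAI in combination with systemic chemotherapy can increase the 15 month RFS", and the Study Objective paragraph of section 1.0 is similar.

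Section 14.0 randomises 78 patients 1:1. It sets an unacceptable 15-month RFS of 50% and an acceptable one of 70%, with type I and type II error of 10% each for a single-stage exact binomial test in each arm. With 24 or more of 39 alive and disease free at 15 months, "the regimen in that arm will be considered worthy of further investigation".

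The arms are then compared by a pick-the-winner rule. One sentence says "The pick the winner role only occurs if both regimens are efficacious". The next says that an arm wins if its count is 24 or higher and "it exceeds by at least 3 patients the number of alive and disease free patients at 15 months in the other arm". The stated chances are 85% for selecting the better regimen, about 9% for selecting none and 6% for a tie.

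RFS and overall survival will also be estimated by Kaplan-Meier. The only log-rank test named is for biomarkers: "Associations between biomarkers and RFS and overall survival will be assessed using the log-rank test".

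**The concern.** There are two problems.

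First, the question and the analysis do not match. Whether RFS increases when panitumumab is added is a question about the difference between two randomised arms. Section 14 answers two other questions: does each arm beat 50%, and which arm would be taken forward. The trial could end with a named winner but no planned statement of the size or uncertainty of the panitumumab effect. Any contrast then reported would have been chosen after the data were seen.

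Second, the two sentences that define the selection step disagree. One requires both arms to be efficacious, and the other requires only the winning arm to reach 24. A decision rule should have one reading before the data are seen.

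**Working it through.** **Inputs.** From section 14.0: n = 39 per arm, threshold 24, lead 3, rates 50% and 70%. From section 3.1.3: 50% is the chosen historical control, and in the centre's most recent HAI study "RFS was 59 % at 15 months". All 39 patients per arm are assumed evaluable at 15 months. X and Y are independent Binomial(39, p) counts for the two arms.

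**1. Per-arm error rates.** P(X ≥ 24 | 0.50) = 0.0998 and P(X < 24 | 0.70) = 0.0944. Both agree with the stated 10%.

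**2. The plan's selection figures at 70% versus 50%.** X is the 70% arm.
- Better arm named: P(X ≥ 24 and X − Y ≥ 3) = 0.846.
- Wrong arm named: P(Y ≥ 24 and Y − X ≥ 3) = 0.007.
- None: P(X < 24) × P(Y < 24) = 0.0944 × 0.9002 = 0.085.
- Tie: 1 − 0.846 − 0.007 − 0.085 = 0.062.

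This gives 84.6/8.5/6.2% against the stated 85/9/6%. The stated figures therefore come from the sentence that requires one arm at 24 or more with a lead of at least 3.

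**3. The both-efficacious sentence taken literally.** Both arms reach 24 with probability 0.9056 × 0.0998 = 0.090. Requiring in addition that the better arm lead by at least 3 leaves 0.049. A winner cannot be named in more than 9.0% of trials on this reading, so it cannot give 85%.

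**4. A softer reading of that sentence.** Suppose that a lone passing arm wins outright and the lead of 3 applies only when both pass. The result at 70% versus 50% is 86.4/8.5/4.0%, a poorer match to 85/9/6%. It differs from the written rule only at 24–22, 24–23 and 25–23, in either direction. Those results have total probability 2.2% at 70% versus 50% and 9.0% if both arms are at 59%.

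**5. Equal arms under the written rule.** P(panitumumab named winner) is the sum over x ≥ 24 and y ≤ x − 3 of b(x; 39, p) × b(y; 39, p):

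| Common 15-month RFS | Panitumumab named winner |
|---|---|
| 48% | 5.4% |
| 50% | 8.1% |
| 55% | 16.7% |
| 59% | 22.9% |
| 65% | 26.9% |
| 70% | 26.8% |

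By symmetry the control arm is named equally often. Section 14.0 gives no equal-arms figure. The 48–70% range is an assumption. It treats 59% as a simple proportion of the 73 patients in that study's column: 1.96 × √(0.59 × 0.41/73) = 0.113, so about 0.48 to 0.70.

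**6. What a minimum win looks like.** With 27 versus 24 of 39, the difference is 3/39 = 7.7 points. The Newcombe 95% CI is −13 to +28 points. The one-sided p is 0.24 by pooled z and 0.32 by Fisher's exact test.

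**7. Precision of a planned difference.** The 95% half-width at 70% versus 50% is 1.96 × √(0.70 × 0.30/39 + 0.50 × 0.50/39) = 1.96 × √(0.46/39) = 0.213, about 21 points.

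**The case against.** **This is a recognised selection design.** Section 14.0 names the randomised phase II selection approach and promises only selection. It defines its type I error as accepting a therapy that is not promising, arm by arm, and never presents 10% as a between-arm error. That stands. A reader might infer from the 23–27% figures that the trial has an inflated false-positive rate or that the rule was miscalculated. The documents support neither: the rule reproduces its stated figures, and such designs do not aim to control that error. At 65–70% both arms are also at or near the protocol's acceptable rate, so taking either forward costs little.

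**The objective may mean the regimen against the historical control.** The Study Objective paragraph and section 2.0 can be read as the whole panitumumab regimen against 50%, which the 24-of-39 rule addresses. That is possible, though not the most natural reading. It does not fit section 1.0's Therapeutic Intervention text, which speaks of adding panitumumab to the background treatment.

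**Kaplan-Meier curves allow a comparison.** They do, but section 14.0 specifies no contrast or interval.

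**The conflicting sentence is only loose drafting.** Probably so, since the stated 85/9/6% shows which rule was meant. A reader might also infer that results such as 24–22 have no defined outcome. Under the written rule they do: the passing arm merits further investigation and no winner is declared. The contradiction still leaves two incompatible statements of when selection applies.

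**Conclusion.** The concern holds in limited form. Section 14.0 plans no between-arm estimate or confidence interval for a primary objective that section 1.0 states as a comparison. A named winner cannot stand in for one: with no panitumumab effect, the rule names panitumumab winner 8% of the time at 50% and 23% at 59%. These figures assume independent arms and complete 15-month status. The 59% is uncertain because section 3.1.3 reports RFS falling as worse-risk patients are accrued. They show what a winner means and are not an error in the design.

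Separately, the both-efficacious sentence contradicts the rule that follows it and is incompatible with the stated 85%: 4.9% if taken literally. This does not depend on the 59%.

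The threshold, lead, sample size and stated operating characteristics are sound. This should be fixed, but it needs no redesign.

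**What to change.** In section 14.0:

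1. Delete or correct the both-efficacious sentence so that it matches the rule behind 85/9/6%: one arm at 24 or more and a lead of at least 3.
2. Pre-specify the difference in 15-month RFS between the arms, in all randomised patients, with a two-sided 95% CI. Label it a supportive estimate that does not change the selection decision.
3. State the equal-arms probabilities beside the rule (8% at 50%, 23% at 59%, about 27% at 65–70%), and say that selection alone does not show that panitumumab increases RFS.

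A hazard ratio with CI is optional. No added log-rank threshold is needed, since a second decision criterion beside the selection rule could give a conflicting message.

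The cost is wording and one small analysis of data already collected, with no extra patients or visits. The drawback is imprecision: at about ±21 points, the estimate is supportive only.

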### Study Population

- Eligible patients (metastatic colorectal cancer with no extra-hepatic disease immediately prior to protocol enrollment) who have liver resection and are all-RAS wild type.

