##### **4.3.2 Planned Experiments**

We will evaluate the genomic profiles of the tumors in an effort to identify markers of sensitivity or resistance to therapy. Primary or liver biopsy tissue will be evaluated for all RAS testing in order to determine eligibility for study. We will test the tumor tissue for all patients for mutations in the RAS/BRAF pathway, among others using a next-generation sequencing platform. Additionally, genomic DNA will be extracted by standard techniques and analyzed using MSK-IMPACT (Wagle et al). This assay uses targeted, massively parallel sequencing to analyze all exons of over 400 genes selected for their known roles in cancer initiation or progression (examples include *APC*, *all RAS*, *BRAF*, *TP53*, *NF1*, etc.). Genomic DNA will be subjected to solution-phase hybrid capture using the RNA baits, followed by massively parallel sequencing. To exclude germline single nucleotide polymorphisms, concurrent analysis of normal tissue DNA will be performed. Somatic alterations, including mutations, insertions and deletions, and copy number changes, detected by this assay will be correlated with clinical parameters.

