## 6.0 CRITERIA FOR SUBJECT ELIGIBILITY

### 6.1 Subject Inclusion Criteria

- History of histologically confirmed colorectal adenocarcinoma metastatic to the liver with no clinical or radiographic evidence of extrahepatic disease. Confirmation of diagnosis must be performed at MSKCC.
- Completely resected hepatic metastases without current evidence of other metastatic disease.
- Lab values  $\leq$  14 days prior to treatment start:
  - WBC  $\geq$  3.0 K/uL
  - ANC  $>$  1.5 K/uL
  - Platelets  $\geq$  100,000/uL
  - Creatinine  $<$  1.5 mg/dL
  - HGB  $\geq$  9 gm/dL
- Renal function ( $\leq$  14 days prior to treatment start).
  - Creatinine  $\leq$  1.5 mg/dL or creatinine clearance  $\geq$  50 mL/min calculated by the Cockcroft-Gault method as follows:
    - Male creatinine clearance =  $(140 - \text{age in years}) \times (\text{weight in Kg}) / (\text{serum Cr in mg/dL} \times 72)$
    - Female creatinine clearance =  $(140 - \text{age in years}) \times (\text{weight in Kg}) \times 0.85 / (\text{serum Cr in mg/dL} \times 72)$  (use of creatinine clearance per protocol based on chemotherapy regimen)
- Hepatic function, as follows: ( $\leq$  14 days prior to treatment start)
  - Aspartate aminotransferase (AST) ( $\leq 5 \times \text{ULN}$ )
  - Alanine aminotransferase (ALT) ( $\leq 5 \times \text{ULN}$ )
  - Total Bilirubin  $\leq$  1.5 mg/dL
- Magnesium  $\geq$  lower limit of normal ( $\leq$  48 hours prior to treatment start)
- Calcium  $\geq$  lower limit of normal ( $\leq$  48 hours prior to treatment start)
- Prior chemotherapy is acceptable if last dose given  $\geq$  3 weeks prior to registration to this study. [Note: no chemotherapy to be given after resection of liver lesions prior to treatment on this study.]
- Any investigational agent is acceptable if administered  $\geq$  30 days before registration
- KPS  $\geq$  60% (ECOG (or Karnofsky) performance status (*preferably 0 or 1* $\geq$  60% for Karnofsky)
- Histologically confirmed all-RAS wild type . Paraffin-embedded tumor tissue obtained from the primary tumor or metastasis (Prior to

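### Biomarkers described as predictive are tested only by a marker-outcome log-rank test, which cannot separate prediction of panitumumab benefit from prognosis

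*Combined protocol and SAP*

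**What the plan says.** - **Aim.** The third secondary objective in Section 2.0 is "to analyze tumor tissue for predictive biomarkers (such as NRAS, BRAF, PIK3CA, AKT1 and MEK1), and correlate with patient progression and survival following therapy". Section 4.3.2 describes the genomic work as done "in an effort to identify markers of sensitivity or resistance to therapy".
- **Method.** Section 14.0 gives the biomarkers one sentence: "Associations between biomarkers and RFS and overall survival will be assessed using the log-rank test". It does not say whether the test is pooled over arms or done by arm. It gives no arm-by-marker interaction, significance level, marker definition, minimum number of carriers or multiplicity rule, and it does not call the work exploratory. No other section supplies these.
- **Population.** Section 1.0 (Study Population) limits entry to patients "who have liver resection and are all-RAS wild type". Section 6.1 requires "Histologically confirmed all-RAS wild type", and Section 4.3.2 says: "Primary or liver biopsy tissue will be evaluated for all RAS testing in order to determine eligibility for study".
- **Panel.** Section 4.3.2 also plans sequencing of "all exons of over 400 genes selected for their known roles in cancer initiation or progression" and says the alterations found will be related to clinical parameters, which it does not name. Section 3.2.5 adds a copy-number array of over 100 genes, planned for PTEN.

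**The concern.** Section 2.0 and Section 14.0 ask different questions. The first asks which patients gain from panitumumab. The second asks whether patients with an alteration do better or worse. A marker can worsen the outlook equally in both arms, and so say nothing about panitumumab, yet give a small log-rank p-value. Conversely, a marker that is harmful with panitumumab and favourable without it can average out to nothing when the arms are pooled. A test within the panitumumab arm alone does not help, because without the control arm a prognostic effect looks the same as a predictive one.

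The trial randomises a concurrent control arm, so the data for the right contrast will exist. What is at stake is how the correlative results are read. Without an interaction estimate, a prognostic association could be taken as grounds for choosing who should receive an anti-EGFR antibody in a later trial.

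There are two side issues. NRAS is the first marker named, although entry is restricted by RAS status. And there is no error control if the large panel is tested against survival.

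**Working it through.** **The plan's own figures.** None is given for biomarkers. The primary rule reproduces: with X the number recurrence-free among 39, P(X ≥ 24) = 0.0998 at 50% and 0.9056 at 70%, against stated error rates of 10% each. Nothing below touches it.

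**Inputs from the documents.** 78 patients, 39 per arm; 15-month RFS of 50% and 70% as design rates (Section 14.0); 59% in the institution's most recent HAI study (Section 3.1.3).

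**Assumed inputs, not in the documents.** Two-sided 5% per test; marker prevalence 20% unless varied; marker hazard ratios as shown; exponential RFS times.
- Setting A: control 15-month RFS 50% or 59%, uniform censoring at 24–60 months, no panitumumab effect in marker-negative patients.
- Setting B: design rates of 50% and 70%, so treatment hazard ratio ln 0.7 / ln 0.5 = 0.515, with 36 months of follow-up for all.

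**Simulation** (at least 1,000 trials per scenario, so Monte Carlo standard error at most √(0.5 × 0.5 / 1000) = 1.6 percentage points). Entries are the share of trials with a significant result.

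| Marker | Setting | Pooled log-rank | Interaction test |
|---|---|---|---|
| Prognostic only, HR 2 in both arms | A | 63–65% | about 6% |
| HR 2 in one arm, 0.5 in the other | A | about 6% | 49–54% |
| Prognostic only, HR 2 | B, prevalence 20% / 50% | 58% / 70% | not run |
| HR 2 with panitumumab, 0.5 without | B, prevalence 20% / 50% | 5% / 4% | not run |
| Panitumumab benefit only in marker-negative | B, prevalence 20% / 50% | 20% / 24% | not run |

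A log-rank test confined to the panitumumab arm still flags the purely prognostic marker in 41% of trials (setting A, 59%). The last row shows that the pooled test sometimes reacts to a predictive marker, but its p-value cannot be told apart from one produced by prognosis.

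**Power of the interaction test.** With D events, prevalence f, 1:1 allocation and hazard-ratio ratio θ, power ≈ Φ(√(D · f(1−f) · 0.25) · ln θ − 1.96). The design rates give 39 × 0.5 + 39 × 0.3 = 31.2 events at 15 months; 62 is assumed for longer follow-up. For θ = 2 and f = 0.20:
- D = 31: √(31 × 0.16 × 0.25) = 1.114; 1.114 × 0.693 − 1.96 = −1.188; power 12%.
- D = 62: √(62 × 0.16 × 0.25) = 1.575; 1.575 × 0.693 − 1.96 = −0.868; power 19%.

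Over prevalence 5–50% the range is 6–28% for θ = 2 and 10–58% for θ = 3. The roughly 50% in the table belongs to θ = 2 / 0.5 = 4, a favourable case.

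**Carriers.** At 5% prevalence an arm of 39 has no carriers with probability 0.95^39 = 0.135, so at least one arm has none with probability 1 − (1 − 0.135)² = 25%. At least one arm has one carrier or none with probability 65%. The interaction is then inestimable or unstable.

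**Multiplicity, independent tests at 5%.** Five named genes: 1 − 0.95^5 = 22.6% per endpoint; four without NRAS: 18.5%. If 400 panel genes were all testable and all null, 400 × 0.05 = 20 false positives per endpoint, or 40 over RFS and OS.

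**The case against.** The case for the plan has several parts.

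- **The objective does not stop at 'predictive'.** Section 2.0 goes on to correlation with progression and survival, and a log-rank test answers that. Section 14.0 speaks only of associations. This stands: a reader might infer that the secondary objective cannot be answered at all, or that prognostic markers will be reported as predicting benefit. The documents support neither. The defect is that nothing in the plan tests the predictive part of the aim.
- **Pooling is inferred.** Section 14.0 does not say the arms are pooled. This limits the headline percentages to one reading, but a by-arm test is not an interaction test either.
- **The panel.** A reader might infer that every one of the 400-plus genes will be log-rank tested, giving about 40 false positives. Section 4.3.2 names neither the test nor the endpoints, and rarely altered genes would not be testable. Forty is an upper illustration only.
- **NRAS.** A reader might infer that NRAS cannot vary. That is too strong. The documents do not define all-RAS gene by gene, the RAS criterion in Section 6.1 breaks off in the copy reviewed, and primary and metastatic tissue can disagree. On the plain meaning of the term, NRAS should be essentially constant, which leaves almost nothing to test.
- **Low power.** An interaction test in 78 patients will miss most real effects. This is true, and it is a reason to label the work hypothesis-generating. It is not a reason to test a different question.

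**Conclusion.** The mismatch is real. Sections 2.0 and 4.3.2 pose a predictive question, and the single test in Section 14.0 cannot separate prediction from prognosis on either reading. For a pooled test at 20% prevalence, a purely prognostic marker of hazard ratio 2 is flagged about ten times as often as by an interaction test (63–65% against about 6%). A marker with opposite effects by arm is found at about the chance rate, against about 50%. Prevalence, hazard ratios, significance level and censoring are all assumptions. The exact percentages move with them, but the logical point does not depend on them.

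The NRAS listing and the absence of error control for the panel are secondary matters that need clarification. This is a correlative aim, and the primary endpoint, decision rule and sample size are unaffected. It should be corrected before the biomarker data are analysed.

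**What to change.** In Section 14.0:

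1. List the prespecified markers and set a minimum number of carriers per arm below which a marker is only described.
2. For each marker that qualifies, fit a Cox model for RFS and for OS with arm, marker and arm-by-marker interaction. Report the interaction hazard ratio with its confidence interval.
3. Reserve 'predictive' for the interaction term, label the log-rank result prognostic, and call the biomarker work hypothesis-generating.
4. Remove NRAS from the markers to be tested, or say why it is kept.
5. If panel genes are tested against RFS or OS, apply the same carrier minimum and report false-discovery-rate q-values.
6. State that interaction power is low, about 12–19% for a hazard-ratio ratio of 2 at 20% prevalence and 31–62 events.

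The cost is a few sentences and a few lines of code, with no new patients, tissue or assays. The downside is that most interaction estimates will be imprecise and some markers will fall below the carrier minimum.
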